4.5 Study size, case selection and case enrolment

The study will enrol 11,000 cases. Sample size for the analysis corresponds to the number of specimens and on average, it is expected that each case will have three specimens. In assessing sample size adequacy, we were conservative assuming that there will be one specimen per case, rather than the expected average of three per case. A sample size of 11,000 is adequate to estimate diagnostic measures (sensitivity, specificity, negative predictive value (NPV) and positive predictive value (PPV)) with high precision if the study will have a positive finding of obtaining sensitivity and NPV values of at least 0.98. Assuming we will observe NPV=0.98 and same number of normal cases by pathologists and COBix algorithm, varying prevalence between 49% and 90% (observed data in seven sites in Table 1), the largest margin of error (1.96 x standard error) for any of the four diagnostic measures is 0.02 so that confidence intervals for all diagnostic measures will be very narrow. This sample size may seem large, but it is essential to deliver comprehensive assessment of the tool across all patient groups and the full range of pathological entities encountered in practice.

The study has been designed with the majority of cases (9,900) coming from retrospective cases, with 1,100 cases being recruited prospectively. Using retrospective cases is appropriate in this setting and ensures the volume of cases can be recruited and examined in the time available. It also ensures rare and unusual entities can be included so we can explore how these are handled by the algorithm. Prospectively recruited cases will be selected sequentially and will allow the study to collect health economics data, including the time taken for pathologists to examine normal biopsies and the broader impact on pathology workflow.

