Selected cases are recruited and the specimen reviewed by the study pathologist for enrollment. The specimens are anonymised at the point of enrollment. The anonymisation process provides a unique case number, a part identifier, a block identifier and a slide identifying number. Where multiple specimens are combined into one block and all appear on one slide the process for anonymization and number is the same, but the slide receives multiple numbers to account for each specimen it contains. The fact that it is a multi-specimen slide is annotated in the study database. The orientation of the WSI will be used to segment the WSI into the component parts prior to the slide being processed through COBix.

At the point of review, the study pathologist provides the diagnosis of each specimen in the case under the anonymized number on the study database. This is the **reference classification and diagnosis**. All cases are therefore enrolled with two pathologist reviews: the reporting pathologist and the study pathologist. These may be the same person. The timings for the health economics study are taken on the first review only.

To ensure representation from all ethnic groups, case selection will be divided between racial groups in the following proportions:

- White Caucasian groups 70%;
- Black, Asian and minority ethnic (BAME) groups, including racial group unknown 30%.

Prospective cases

Each site enrolls one hundred sequential large bowel biopsy cases prospectively after the study starts.

Retrospective cases

Nine hundred cases are enrolled from the pathology archives at each site. Of these 100 cases is reserved for the categories of rare and unusual diagnoses. The remaining 800 cases are collected sequentially from a time period chosen by the enrolling site.

Classification of specimens

At enrolment, each specimen is classified by the recruiting pathologist into one of the categories shown below:

Diagnostic categories

- 1) **Normal** (any specimen which contains no evidence of disease)
- 2) **Non-neoplastic non-urgent** (any non-neoplastic abnormality which does not have acute inflammation - necrosis or ulceration)
- 3) **Non-neoplastic urgent** (any non-neoplastic abnormality which includes either acute inflammation or necrosis or ulceration)
- 4) **Neoplastic – non-urgent** (any neoplastic lesion which does not include either invasive carcinoma or other form of malignancy or high-grade dysplasia)

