- 5) **Neoplastic urgent** (any neoplastic lesion which includes either high grade dysplasia or invasive carcinoma or other malignant diagnosis)

These categories match then the classification tree in figure 4.

All H&E slides from a case will be seen by the algorithm, but diagnostic categorisation will be done at the specimen level within a case.

[figure not shown]

Figure 4 is a schematic diagram of the COBIx biopsy classification tree depicting how specimens will be classified in the study.

Both pathologists and COBIx classifies each specimen enrolled into one of the five diagnostic categories shown.

Case selection

Each site collects 1000 cases for the study in the following manner:

First, a search of the pathology archive for any of the diagnoses of interest (Cases of interest) listed below of any age and as many of these cases as can be found number X.

Second, a series of cases 900-X from any time period prior to August 2023 using an enrichment process to ensure 30% of cases come from minority ethnic groups, remaining cases are collected sequentially.

Third, a series of 100 cases collected during the trial period to be arranged with the coordinating centre.

Cases of interest, and other interesting and educational cases discovered during the course of the study, will be configured into a training set for the RCPATH Portal.

For the cases enrolled into this study the site will review and ascertain the diagnosis of each specimen and categorise this into one of the 5 categories using the definitions provided.

This work is to be supervised by the principal investigator for the site, the work may be delegate to other staff (trainee pathologists, biomedical scientists, medical students etc. providing they have sufficient training and knowledge and are adequately supervised in this work) as appropriate.

Inclusion criteria

Large bowel endoscopic biopsies from adult patients (over 18 years)

Exclusion criteria

Specimens which are not from large bowel endoscopic biopsies

Incomplete cases with lost slides

Cases from person opting out via the NHS Data opt-out scheme

Faded or damaged slides

Incomplete or missing meta data

The following metadata is required for each case:

Site code

Laboratory number

Ethnic group

Gender

Age group

Procedure type

Tissue Type

Date of biopsy

Colonoscopy report

Clinical details

Specimen parts

Specimen blocks

Macroscopic report

Microscopic report

Diagnosis

SNOMED Code

Scanner type

Image resolution

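### Section 4.5 gives two incompatible rules for drawing the 900 retrospective cases per site, and no listed data item records how a case was selected

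*Protocol*

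**What the plan says.** Protocol Section 4.5 sets the totals: "The study will enrol 11,000 cases", and "The study has been designed with the majority of cases (9,900) coming from retrospective cases, with 1,100 cases being recruited prospectively". It then gives the retrospective rule twice.

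- **Retrospective cases:** the site supplies 900 archive cases. On the rare ones the text reads "Of these 100 cases is reserved for the categories of rare and unusual diagnoses"; for the others it reads "The remaining 800 cases are collected sequentially from a time period chosen by the enrolling site".
- **Case selection:** "First, a search of the pathology archive for any of the diagnoses of interest (Cases of interest) listed below of any age", taking "as many of these cases as can be found number X". Next come 900-X cases dated before August 2023, "using an enrichment process to ensure 30% of cases come from minority ethnic groups, remaining cases are collected sequentially".

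A 70/30 ethnic split also stands in Section 4.5 ahead of both the prospective and the retrospective subheadings, and there patients of unknown racial group count toward the 30%. The Case selection text does not mention them. The prospective 100 per site are called sequential in one place. In the other they are only to be arranged with the coordinating centre.

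Table 2 lists the metadata required for each case. It includes ethnic group, biopsy date, diagnosis and SNOMED code, but no item for the route by which the case was selected. Section 6 acknowledges that enrichment makes the study prevalence unrepresentative, sets a bar of 0.98 for sensitivity and NPV, and plans a subgroup analysis by ethnicity.

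**The concern.** A site that follows the Case selection steps does not obtain the series described under Retrospective cases. The rare count is either fixed at 100 or open-ended. The series is either 800 or 900-X. It is either plainly sequential or quota-selected. Eleven sites could follow different rules in good faith, and an analysis plan cannot undo how cases were drawn.

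Three things are at stake. First, the sequential retrospective cases are the largest set that could show performance at routine case mix, and they may not be identifiable afterwards. Second, where minority patients are few, filling the quota means reaching further back in the archive for them than for White patients, which could affect the ethnicity subgroup. Third, listed entities that fall inside the sequential window are counted in the rare set instead, so a readout of the sequential cases alone would be short of them.

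**Working it through.** **1. The protocol's own split.** 11 × 900 = 9,900; 11 × 100 = 1,100; the sum is 11,000. Per site, 900 − 100 = 800. This reproduces.

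**2. Series size under Case selection.** Series = 900 − X per site. X is not given, so these values are assumptions.

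| X | Series per site | Over 11 sites |
|---|---|---|
| 50 | 850 | 9,350 |
| 100 | 800 | 8,800 |
| 200 | 700 | 7,700 |
| 300 | 600 | 6,600 |

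Only X = 100 gives 800.

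**3. Effect of the quota at X = 100.** Let S be the consecutive cases, T the minority top-ups and p the natural minority share (not in the protocol, so assumed). Then S + T = 800 and pS + T = 0.30 × 800 = 240. Subtracting gives S = 560/(1 − p). The archive run needed to yield 240 minority cases is 240/p. The run needed to yield the 560 others is 560/(1 − p), the same as S.

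| p | S | T | Run for 240 minority cases | Run for 560 others |
|---|---|---|---|---|
| 5% | 589 | 211 | 4,800 | 589 |
| 10% | 622 | 178 | 2,400 | 622 |
| 20% | 700 | 100 | 1,200 | 700 |
| 30% | 800 | 0 | 800 | 800 |

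For scale, Table 1 gives Coventry 4,877 large bowel biopsies in 2019. If those counts are cases, p = 5% means 4,800/4,877, about a year, for the minority cases against 589/4,877 = 0.12 year, about six weeks, for the others.

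If unknown racial group counts toward the 30%, its share adds to p. For example, 10% minority plus an assumed 10% unknown gives 560/0.80 = 700 consecutive cases rather than 622.

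**4. Depletion at X = 100.** If 100 listed cases are taken from an archive of N cases, a window of 800 loses about 100 × 800/N of them. Assume a 10-year archive at Coventry's volume, the lowest in Table 1: N = 48,770 and the loss is 1.6 cases. At 65.5% abnormal (Table 1: 34.5% normal) the window holds 524 abnormal cases, so the loss is 1.6/524 = 0.3% of them. Assume sensitivity 0.80 on these entities and 0.985 on the rest. Sensitivity in the sequential set then shifts by 0.0031 × 0.185 = 0.0006. A 5-year archive (N = 24,385; loss 3.3) gives 0.0012. A one-year archive (N = 4,877; loss 16.4) would give 0.0058, but the search is not limited by case age.

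**5. What an identifiable consecutive set adds.** Take one specimen per case, 65.5% abnormal, and sensitivity and NPV of 0.98. For NPV, use the protocol's assumption of equal numbers called normal by pathologist and algorithm.

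- Prospective only: 1,100 × 0.655 = 720 abnormal; sensitivity margin 1.96 × √(0.0196/720) = 0.010. With 1,100 × 0.345 = 380 normal, NPV margin 1.96 × √(0.0196/380) = 0.014.
- Adding 11 × 589 = 6,479 consecutive cases gives 7,579: 4,964 abnormal, sensitivity margin 0.004; 2,615 normal, NPV margin 0.005.

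**The case against.** The case for leaving this alone is substantial. Enrichment is deliberate and disclosed, and Section 6 asks for very high NPV whatever the case mix. The Case selection text itself confines sequential collection to the remaining cases. The planned sensitivity and NPV are pooled, and the swept rare cases stay in that pool, so nothing difficult is lost from the primary result. Biopsy date, diagnosis, SNOMED code and ethnic group are all collected, so much could be reconstructed. Faded slides are excluded and stain problems are screened for, which limits any effect of slide age.

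Most of that stands, and it rules out several stronger readings that a reader might infer:

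- **That the series cannot be sequential at all.** It can be sequential within ethnic strata, and at a site with about 30% minority patients the quota does not bind.
- **That only the 1,100 prospective cases reflect routine case mix.** The 70/30 split may cover them too as written, and an ethnic quota shifts diagnostic mix only if ethnicity is related to diagnosis, which the protocol does not show.
- **That the sweep lifts the sequential cases over the 0.98 bar.** This needs listed entities to be common and nearly all removed. At an assumed 3% of cases in a 10-year Coventry archive there would be 0.03 × 48,770 = 1,463. A fixed 100 removes about 7% of them, and an uncapped sweep exceeds 900 and leaves no series.
- **That the workload estimate is distorted by the sweep.** Specificity is computed among normal specimens, so moving rare abnormal ones leaves it unchanged.

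The objection does not remove the contradiction. Nor is reconstruction dependable. Several entities in Table 3 have no SNOMED code, the enrichment method is not described, and without a route flag or fixed window dates a minority case cannot be reliably assigned to the run or to the top-up.

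**Conclusion.** The two descriptions in Section 4.5 conflict on the rare count, the series size, the use of a quota and who counts toward it, and they need to be reconciled. The figure of 800 holds only at X = 100. At assumed natural minority shares of 5% to 20%, between 589 and 700 of those 800 would form a consecutive run, and more if unknown racial group counts toward the 30%. Minority cases may come from a longer archive span than White cases. That is a possible, unquantified complication for the ethnicity subgroup.

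Depletion of the window by the rare sweep is of unknown size and probably small if X is about 100. It touches only a readout of the sequential cases, which the protocol does not currently plan. The pooled result is not shown to be biased by any of this. The minority shares, X, archive lengths and rare-entity sensitivities are all assumptions. The change is worth making because it is cheap and preserves a large set for showing performance at routine case mix.

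**What to change.** Replace the two descriptions with one rule:

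1. The coordinating centre fixes a start date for each site. The site enrols every eligible case consecutively from that date, whatever the diagnosis or ethnicity.
2. Rare-entity and ethnicity top-ups are then drawn to reach 900, taking White and minority top-ups from the same archive span where possible. Any White top-ups come out of the 560 in step 3 of the working, so the consecutive number falls accordingly.
3. Add a selection-route item to Table 2: consecutive, rare, ethnicity top-up or prospective.
4. State the expected consecutive number in place of 800, say whether unknown racial group counts toward the 30%, and say whether the 70/30 split applies to the prospective cases.
5. Report sensitivity, specificity, NPV and PPV in the consecutive plus prospective cases alongside the pooled result.

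Total enrolment does not change. The cost is one extra field per case and, for cases already enrolled, a check by biopsy date to assign the flag. That check will be less certain for quota cases than for rare ones.

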4.6 COBix algorithm analysis of the study slides

Once the cases have been anonymized, the WSIs and clinical metadata are transferred to the COBix study section of the Tissue Image Analytics (TIA) Centre. The slides are then queued for processing through the COBix algorithm. The COBix classification of the specimens is added to the database and an automated lookup table compares the results to the reference diagnosis. Discrepant results are queued for pathologist re-review and ground truth diagnosis. TIA Centre will be working with Histofy Ltd for generating the predictions for the model. The TIA Centre will also be able to request non-diagnostic technical metadata for the cases received for the study from Warwick CTU as needed.

Before the slides are processed by COBix algorithm, an automated image quality control (iQC) will be run on all the slides. The main purpose of this iQC check will be to identify images of insufficient quality to be processed by COBix and would need to be rescanned or replaced. The checks will include detection of sufficient tissue area, blur, out of focus, tissue folding, and stain issues.

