The PathLAKE project has created the prototype, on a dataset of over 8,000 WSIs of large bowel biopsies, with slide level diagnosis on 5,107 slides, divided into training and test sets (60% and 40% respectively). Using the IDARS algorithm alone at x5 magnification equivalent images, and hence only architectural morphological features, we have already achieved excellent separation of normal from neoplastic lesions and abnormal, both neoplastic and non-neoplastic lesions (see Figure 2).

Pathologist ground truth data, in triplicate on 150 selected slides has generated over 250,000 annotations that have been processed and added to the original model of Hover-Net¹¹ (see Figure 3). This is the largest dataset for nuclear instance segmentation in existence, with nearly half a million labelled nuclei in colon tissue¹² (Figure 3).

[figure not shown]

Figure 3 Selected fields of region and cell level annotation made by the Iguana algorithm which has been developed using pathologists' annotation of diagnostic regions and patched of cell level annotation in the training set of slides.

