4.4 The Multi-site validation study outline

The study aims to recruit 11,000 patient cases from adults across 11 separate centres in the UK. All the H&E stained slides (from approximately 33,000 specimens) from these cases will be scanned (or in some cases, have already been scanned) to digital WSIs at the recruiting site using equipment used for routine diagnosis. Scanned images will be anonymised and transferred electronically to a storage housed within the TIA Centre. Once these digital slides have been transferred, they will be processed through the COBix algorithm and classified into one of the three main categories and four subcategories. The results of the algorithm classification will be compared to the reference pathologist diagnosis.

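### The eligibility rules do not keep cases used to develop COBI/COBix out of the validation set

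*Protocol*

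**What the plan says.** **Case sources (Protocol 4.4 and 4.5).** Of 11,000 cases, 9,900 are retrospective and 1,100 prospective. Each site searches its archive for cases of interest of any age, then adds "a series of cases 900-X from any time period prior to August 2023". Slides are scanned for the study "or in some cases, have already been scanned".

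**Exclusions (4.5).** There are five: specimens that are not large bowel endoscopic biopsies, incomplete cases with lost slides, NHS data opt-outs, faded or damaged slides, and incomplete metadata. None concerns earlier use in development.

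**Development data (4.2).** The prototype was built "on a dataset of over 8,000 WSIs of large bowel biopsies", of which 5,107 had a slide-level diagnosis. Source hospitals and dates are not given.

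**Ownership (8.1 and 14).** UHCW sends study images to the TIA Centre and holds the existing intellectual property jointly with the University of Warwick.

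**Data flow (4.6).** "Once the cases have been anonymized, the WSIs and clinical metadata are transferred to the COBix study section" of the TIA Centre, and then: "The slides are then queued for processing through the COBix algorithm". Later in the same section the TIA Centre "will also be able to request non-diagnostic technical metadata for the cases received for the study". The only list of metadata fields is in 4.5, introduced by "The following metadata is required for each case" (Table 2). It includes Diagnosis, Microscopic report and SNOMED Code.

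**Success criterion (6).** Sensitivity and NPV must both be above 0.98.

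**The concern.** A validation estimate describes new patients only if the algorithm has not already met the validation cases. A model tends to do better on slides it was fitted to, and somewhat better on slides used to choose a threshold or a version. If such slides re-enter, false negatives are too few, and sensitivity and NPV come out too high. Enrolling more cases does not remove this bias.

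The stakes come from the intended use. Section 4.2 has a normal result trigger an automated report that a pathologist would not ordinarily check, and section 4.1 offers this study as the evidence for regulatory approval. Independence should therefore be visible in the eligibility rules.

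**Working it through.** The protocol gives no figure for overlap, so there is none to reproduce. The check has two parts.

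**1. Do the rules as written admit development cases?**
- A development slide from an adult's large bowel biopsy at a participating site, dated before August 2023, intact and with full metadata, meets the inclusion criterion and none of the exclusions (apart from a data opt-out).
- There is no early date limit that would separate the two sets, and prior scanning is no bar.
- Section 6 says that COBix is developed before the study begins. This protects the 1,100 prospective cases at slide level, but not archived slides, which can predate both.
- So up to 9,900 / 11,000 = 90% of cases fall under rules that permit overlap. This is the share exposed, not an estimate of overlap.

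**2. How large could the bias be?** Let f be the share of abnormal specimens also used in development:

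observed sensitivity = f × s_seen + (1 − f) × s_unseen

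Assumed, because the protocol gives neither: s_seen = 1.00, and s_unseen = 0.975 to 0.978.

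*One whole site:* f = 1,000 / 11,000 = 0.091.
- s_unseen = 0.975: 0.091 + 0.909 × 0.975 = 0.9773, a shift of 0.0023.
- s_unseen = 0.978: 0.091 + 0.909 × 0.978 = 0.9800, a shift of 0.0020.
- Counting only that site's 900 retrospective cases, f = 0.082, and 0.98 is reached from s_unseen = 0.9782.

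Unseen sensitivity at which the pooled value equals 0.98, that is (0.98 − f × s_seen) / (1 − f):

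| f | s_seen = 1.00 | s_seen = 0.995 |
|---|---|---|
| 2% | 0.9796 | 0.9797 |
| 5% | 0.9789 | 0.9792 |
| 9.1% | 0.9780 | 0.9785 |
| 20% | 0.9750 | 0.9763 |

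*Re-entry of the development slides themselves,* taking about 33,000 specimens (4.4), one slide per specimen, a similar case mix and s_unseen = 0.975:
- About 3,400 training slides (4.1): f = 3,400 / 33,000 = 10.3%, observed 0.9776.
- All 5,107 labelled slides (4.2): f = 5,107 / 33,000 = 15.5%, observed 0.9789.

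*Comparison with sampling error:* Table 1 has 34.5% normal, so one specimen per case gives 11,000 × 0.655 = 7,205 abnormal specimens. Then 1.96 × √(0.98 × 0.02 / 7,205) = 0.0032. A bias of 0.002 is smaller than this margin.

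**The case against.** The strongest reply is that no overlap is shown and that safeguards exist. COBix is fixed before the study, the threshold is pre-specified from external data, and WCTU finds the discrepancies and determines performance (4.7 and 6). These points stand, but none of them stops an archived development slide from being enrolled.

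Several stronger readings are not supported:

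- **That development and validation slides are mixed.** The protocol shows only that overlap is not prevented. Co-owning the algorithm is not evidence of shared slides, and nothing shows that rare entities are the likeliest overlap.
- **That the developer receives the diagnoses before running COBix.** Appendix 16.1 does link the TIA Centre and Histofy to COBix development, and they generate the predictions. But no section says that the diagnosis is transferred. Table 2 lists Clinical details separately from Diagnosis, sections 4.4 and 8.1 describe only images going to the TIA Centre, and the pathway figure that might settle the matter is not available here.
- **That 4.6 contradicts itself.** The sentence "The TIA Centre will also be able to request non-diagnostic technical metadata for the cases received for the study from Warwick CTU" adds a permission. It hints that WCTU holds the diagnostic fields, but it does not limit the initial transfer.
- **That knowing the diagnosis would bias the result.** A fixed algorithm run on an image gives the same output whoever runs it. The opening is narrower: section 6 speaks of scores from more than one variant of the algorithm, so a single locked version is not clearly described.
- **That overlap could not be found later.** Laboratory number is required metadata, and 4.7 relies on tracing cases back to sites.
- **That overlap would carry COBix past the bar.** From 0.975, a 20% overlap gives exactly 0.980, while section 6 requires a value above 0.98. Re-entry of every labelled slide stays below it.

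**Conclusion.** The point holds as a gap in the eligibility rules. As written, they admit cases used to develop COBI/COBix, and the protocol gives no source for the development slides that would rule this out. Actual overlap is unknown.

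If overlap exists, the bias is upward and modest: about 0.2 percentage points of sensitivity for one fully overlapping site, given perfect reading of seen slides. In that scenario the conclusion changes only if unseen sensitivity lies between about 0.978 and 0.980. NPV moves in the same direction, by an amount that depends on case mix. The case for acting rests on the purpose of the study and the low cost of the protection, not on a demonstrated distortion.

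The metadata question is a secondary clarification: an undefined term, combined with the reference to several variants.

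**What to change.** 1. **Section 4.5, exclusion criteria.** Exclude any patient whose slides were used in training, tuning, threshold-setting or testing of COBI/COBix. The site checks this by laboratory number before anonymisation. Working at patient level also covers a new biopsy from a patient whose earlier slides were used.
2. **Section 4.6.** Define the fields sent to the TIA Centre and Histofy. State that Diagnosis, Microscopic report and SNOMED Code are held at WCTU until predictions from the locked Version 1.0 are lodged there. Align section 6 so that the primary analysis refers to that version alone.

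**Cost.** Protocol wording, a data-transfer specification, and a one-off list match at any site that supplied development slides. A few rare cases may be lost. If there is no overlap, the match documents it.
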